APPENDIX F SPECIMEN REQUISITION79

1. OBJECTIVES

1.1 Study Design

This is a randomized, two-arm phase II study of neratinib with or without fulvestrant in patients with metastatic, ER-positive/HER2-positive breast cancer. We hypothesize that crosstalk between HER2 and ER signaling pathways provides escape mechanisms for tumor growth, and therefore tumors that are both HER2-positive and ER-positive can be effectively treated with neratinib in combination with fulvestrant, and that the combination will be more effective than neratinib alone.

1.2 Primary Objective

To estimate the efficacy, as measured by progression free survival (PFS), of neratinib combined with fulvestrant compared with neratinib alone in patients with inoperable locally advanced or metastatic HER2-positive, ER-positive breast cancer.

1.3 Secondary Objectives

- 1.3.1 To estimate the efficacy, as measured by overall survival (OS) of neratinib combined with fulvestrant compared with neratinib alone in patients with inoperable locally advanced or metastatic HER2-positive, ER-positive breast cancer. (ENDPOINT: OS)
- 1.3.2 To estimate the clinical activity, as measured by overall response rate (ORR) of neratinib combined with fulvestrant compared with neratinib alone in patients with inoperable locally advanced or metastatic HER2-positive, ER-positive breast cancer. (ENDPOINT: ORR)
- 1.3.3 To estimate the clinical activity, as measured by duration of response, of neratinib combined with fulvestrant compared with neratinib alone in patients with inoperable locally advanced or metastatic HER2-positive, ER-positive breast cancer. (ENDPOINT: duration of response)

1.4 Correlative Objectives

- 1.4.1 To determine the proportion of patients with ESR1 gene mutations in baseline tumor tissue
- 1.4.2 To determine the proportion of patients with PIK3CA gene mutations and loss of PTEN expression in baseline tumor tissue
- 1.4.3 To determine the proportion of patients with PIK3CA gene mutations in circulating tumor DNA (ctDNA) from blood obtained at study baseline

- 1.4.4 To determine concordance of PIK3CA mutation status assessed in circulating free tumor DNA and distant metastasis specimens (i.e. liquid and solid biopsies)
- 1.4.5 To determine concordance of ESR1 mutation status assessed in circulating free tumor DNA and distant metastasis specimens (i.e. liquid and solid biopsies)
- 1.4.6 To perform molecular characterization of potential resistance mechanisms, predictive biomarkers, and immunological function by collecting blood and tumor specimens.

2. BACKGROUND

2.1 Metastatic HER2-Positive, ER-Positive Breast Cancer

Breast cancer is the most common malignancy in women in the United States. Every year, more than 230,000 women are diagnosed, and more than 40,000 women die of breast cancer.¹ Most of these deaths are due to metastatic breast cancer. Though existing treatments may effectively control disease for a period of time, nearly all tumors will acquire resistance to therapy, leading to tumor growth and eventually death. More effective treatments are needed. Approximately two-thirds of breast cancers express the estrogen receptor (ER), and hormone-directed treatment has been a mainstay of therapy for such cancers for decades. Human epidermal growth factor receptor-2 (HER2) overexpressing tumors account for 20-25% of breast cancers, and are associated with high grade tumors, higher rates of recurrence, and higher rates of brain metastases. Anti-HER2 therapies have transformed the trajectory of HER2-positive disease, improving patients' outcomes dramatically. Approximately 10% of all breast cancers co-express HER2 and ER. Though these HER2+/ER+ tumors make up a significant portion of metastatic breast cancers, they have historically been studied together with HER2+/ER- disease, meaning that patients with HER2+/ER+ disease usually receive HER2-directed treatment in combination with chemotherapy. There is reason to believe, however, that because of crosstalk between HER2 and ER signaling pathways, blockade of both may be more effective.

2.2 Neratinib

Neratinib is a potent, oral, irreversible-binding inhibitor of the erbB family of receptor tyrosine kinases that inhibits signal transduction through erbB1 (EGFR), erbB2 (HER2), and erbB4. The irreversible binding of these receptors by neratinib results in sustained inhibition of growth pathways (autophosphorylation, signal transduction, and cell proliferation) and ultimately cell cycle arrest at the gap 1/DNA synthesis (G1/S) phase transition of the division cycle. This agent has demonstrated promising clinical activity in patients with HER2-positive breast cancers.²

In a phase II trial of neratinib for patients with HER2-positive, metastatic de-novo or pre-treated breast cancer, the ORR (defined as complete or partial responses) was 51% (95% Confidence Interval [CI] 16% to 39%) and 26% (95% CI 38% to 64%), respectively. At 16 weeks, 75% of first-line patients and 61% of previously treated patients were progression-free.³ In a subsequent, randomized phase two study comparing neratinib monotherapy to lapatinib plus capecitabine in previously treated metastatic breast cancer, the ORR was 29% in the neratinib arm.⁴ The major

toxicity of neratinib in all studies has been diarrhea, which is most common during the first cycle of treatment.

2.3 Fulvestrant

Fulvestrant is a selective estrogen receptor degrader (SERD), which binds to ER and leads to its degradation. It is FDA approved for patients who have disease progression on other anti-estrogen agents in the advanced breast cancer setting. In two phase III trials, fulvestrant 250 mg monthly was found to be as effective as anastrozole with respect to disease progression and overall survival.^{7,8} In the CONFIRM trial, high-dose fulvestrant at 500 mg monthly was found to be more effective compared to the previous dosing of 250 mg monthly, which prompted the FDA's subsequent approval of fulvestrant 500 mg every 28 days, following a loading dose of 500 mg on days 1 and 15 during the first month of therapy for refractory metastatic breast cancer.⁹

Overall, fulvestrant demonstrated an overall response rate of approximately 10% in aromatase inhibitor resistant, fulvestrant naive ER+ HER2- breast cancers.⁹ In a retrospective study of patients with HER2+/ER+ breast cancer, fulvestrant demonstrated an overall response rate of 9% and clinical benefit rate of 42% (43/101 patients), with anti-tumor activity observed in up to the fourth line of endocrine therapy and seventh line of overall therapy.¹⁰

2.4 Rationale

HER2 is a member of the HER/EGFR family of plasma membrane-bound receptor tyrosine kinases. HER2 dimerizes with itself or other members of the HER family, leading to its activation and subsequent downstream growth-promoting signaling via a number of pathways. Investigation of mechanisms of resistance to hormone-directed therapy in breast cancer has demonstrated significant crosstalk between the HER2 and ER pathways. In HER2-positive cell lines, addition of estrogen or tamoxifen induces activation of HER2 signaling.¹¹ In ER+ cell lines that develop resistance to tamoxifen, HER2 expression increases significantly.¹² And in HER2+ xenografts resistant to HER2-directed therapies, ER expression is upregulated.¹³ These data suggest that ER-mediated signaling may provide an important mechanism of resistance to anti-HER2 therapy, and conversely, that HER2-signaling promotes endocrine therapy resistance. Dual blockade of HER2 and estrogen pathways could be an effective method of treating HER2+/ER+ disease.

Data from clinical studies supports what has been seen in the laboratory. Rimawi and colleagues evaluated the efficacy of neoadjuvant lapatinib, trastuzumab and hormonal therapy in a single-arm, phase II study of 66 women with stage II to III HER2+/ER+ breast cancer.¹⁴ They found that this combination, targeting both the HER2 and ER pathways, was effective, resulting in a pathologic complete response (pCR) rate of 21%.¹⁴ In 2015, Chan et al. presented 2 year follow up data from the ExteNET trial, a phase III, randomized, placebo-controlled trial of neratinib after completion of trastuzumab in the adjuvant setting in HER2+ breast cancer. In this study, early stage breast cancer patients with HER2+ disease who had completed adjuvant trastuzumab were randomized to receive either one year of neratinib or placebo. Of the 2841 patients enrolled in this study, 57% in each arm had HER2+/ER+ disease. Though the improvement in invasive disease-free survival (IDFS) was statistically significant in the overall study population, in a pre-

planned subset analysis, the strongest benefit was seen in the centrally confirmed HER2+, ER+ subgroup. In this group, patients receiving neratinib had an IDFS of 97.0% at 2 years, while IDFS in patients receiving placebo was 88.4%, corresponding to a hazard ratio of 0.25 (95% CI 0.12-0.48).¹⁵ In contrast, the hazard ratio for patients with centrally confirmed HER2+, ER- cancers was 0.96 (0.53–1.74). Importantly, nearly all patients with HER2+/ER+ disease were also taking adjuvant hormonal therapy. One potential mechanistic explanation of these results is that targeting both the HER2 and ER pathways simultaneously may overcome resistance mediated by the cross-talk between the two pathways. If true, this approach may be an effective method for treating HER2+/ER+ breast cancer. We plan to investigate this further in this trial.

Rationale for Prior Fulvestrant (Amendment 2, Protocol Version 2 update)

The protocol was updated with Version 2 to allow for prior fulvestrant, a revision to the original eligibility criteria (3.2.3) for the study. Internal data from [REDACTED] in mouse models and additional pre-clinical data from Sudhan et al. in *Clinical Cancer Research* suggests that even in fulvestrant resistant HER2+ models, the addition of fulvestrant to neratinib provides benefit.¹⁶ Allowing prior fulvestrant will increase the eligible patient population and study accrual and will not significantly impact the therapeutic signal in the experimental arm.

2.5 Correlative Studies Background

2.5.1 Circulating Tumor DNA (ctDNA)

For a number of reasons that include discomfort to the patient, logistics, and lack of clinical indication, serial tumor biopsies in individual patients in the metastatic setting are infrequently done. It has therefore been challenging to study the molecular evolution of tumors over time and through progression on serial treatment regimens. Both normal and malignant cells secrete cell-free DNA into plasma, generating an easily accessible repository of each cell's genetic signature. Emerging technology now permits whole exome sequencing from circulating tumor DNA (ctDNA) isolated from plasma. We aim to examine the utility of this approach for detecting molecular changes in individual patients' tumors over time by collecting and analyzing ctDNA.

2.5.2 Tissue Samples

We will collect new metastatic biopsies before treatment begins from all enrolled patients unless there is no safe, accessible site to biopsy. (Please see eligibility criteria). We will also collect primary, archived tumors and archived biopsies of metastases for additional correlative testing. These samples will be banked for future research using state-of-the-art technologies to correlate findings with clinical response.

3. PARTICIPANT SELECTION

Laboratory tests required for eligibility must be completed within 4 weeks prior to registration. Scans and x-rays must be done ≤ 4 weeks prior to registration. MUGA or echo must be done within 60 days prior to registration.

3.1 Eligibility Criteria

Participants are eligible to be included in the study only if they meet all of the following criteria:

- 3.1.1 Participants must have histologically or cytologically confirmed inoperable locally advanced or metastatic ER+ breast cancer. To fulfill the requirement for ER+ disease, a breast cancer must express, by immunohistochemistry (IHC), ER in $\geq 10\%$ of cells, on the most recent biopsy. If ER quantification is not available, a determination of ER+ by IHC will suffice. Central confirmation of ER status is not required.
- 3.1.2 Participants must have documented HER2+ disease by overexpression and/or gene amplification on the most recent biopsy, per current ASCO-CAP (American Society of Clinical Oncology – College of American Pathologists) guidelines. Central confirmation of HER2 status is not required.
- 3.1.3 Participants must have received prior therapy with the following agents in any combination, and in setting (i.e., neoadjuvant, adjuvant, metastatic, etc.). These therapies do not need to be the most recent line of therapy.
 - Trastuzumab
 - Pertuzumab
 - Ado-trastuzumab emtansine (T-DM1)
- 3.1.4 Participants must agree to undergo a research biopsy of a reasonably accessible metastatic lesion (chest wall, skin, subcutaneous tissue, lymph nodes, skin, breast, bones, lung, and liver metastases). If a reasonably accessible metastatic lesion is not available, the patient may go on study provided that archived tissue is available. However, if a reasonably accessible site is available for biopsy, the patient must agree to biopsy. Any patients not undergoing biopsy must be approved for study enrollment by the Overall Principal Investigator at DFCI. Biopsies may be done with local anesthesia or intravenous conscious sedation, according to institutional guidelines. If a biopsy requires general anesthesia, then it is only allowed if acquisition of tissue is clinically indicated, and excess tissue may be collected for research purposes. Patients without sites available for biopsy must have available tissue [archived formalin-fixed paraffin embedded blocks (FFPB), blocks from which slides can be created, or fresh frozen tissue from original diagnosis or metastatic setting] for correlative studies. Tissue needs to be located and available at the time of registration See Section 9.3 for more details.
- 3.1.5 Women ≥ 18 years of age. Men are not eligible.
- 3.1.6 Eastern Cooperative Oncology Group (ECOG) performance status 0-2 (see Appendix A).
- 3.1.7 Participants must have normal organ and marrow function as described below:
 - Absolute neutrophil count $\geq 1,000/\mu\text{L}$
 - Platelets $\geq 75,000/\mu\text{L}$
 - Hemoglobin $\geq 8\text{g/dL}$

- Total bilirubin ≤ 1.5 X institutional upper limit of normal (ULN) ;in case of known Gilbert's syndrome, <2 x ULN is allowed
- AST(SGOT)/ALT(SGPT) ≤ 3 X institutional ULN without liver metastases, or ≤ 5 X institutional ULN with liver metastases
- Creatinine clearance ≥ 50 mL/min
- Left ventricular ejection fraction $\geq 50\%$, as determined by RVG (MUGA) or echocardiogram (ECHO) within 60 days prior to initiation of protocol therapy

- 3.1.8 Participants may have received any number of prior therapies as long as they have adequate performance status and meet all other eligibility criteria.
- 3.1.9 Women of childbearing potential (including premenopausal women and women less than 12 months after menopause) must have a negative β -human chorionic gonadotropin (hCG) urine pregnancy test within 4 weeks of registration.
- 3.1.10 The effects of neratinib and fulvestrant on the developing human fetus are unknown. For this reason and because SERD agents are known to be teratogenic, women of childbearing potential must agree to be abstinent, or to use a highly effective double barrier method of contraception (e.g, a combination of male condom with an intravaginal device such as the cervical cap, diaphragm, or vaginal sponge with spermicide) or a non-hormonal method, while enrolled in the study, until at least 28 days after the last dose of neratinib or 1 year after the last dose of fulvestrant. Should a woman become pregnant or suspect she is pregnant while she is participating in this study, she should inform her treating physician immediately. If a woman is of childbearing potential, she must agree to use adequate contraception prior to the study, for the duration of study participation, and for one year after completion of the study drug.
- 3.1.11 Ability to understand and willingness to sign a written informed consent document.

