4. REGISTRATION PROCEDURES

4.1 General Guidelines for DF/HCC Institutions

Institutions will register eligible participants in the Clinical Trials Management System (CTMS) OnCore via the Office of Data Quality. Registrations must occur prior to the initiation of protocol therapy. Any participant not registered to the protocol before protocol therapy begins will be considered ineligible and registration will be denied.

An investigator will confirm eligibility criteria and a member of the study team will complete the protocol-specific eligibility checklist.

Following registration, participants may begin protocol therapy. Issues that would cause treatment delays should be discussed with the Overall Principal Investigator (PI). If a participant does not receive protocol therapy following registration, the participant's registration on the study must be canceled. Registration cancellations must be made in OnCore as soon as possible.

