4.3 General Guidelines for Other Investigative Sites

Eligible participants will be entered on study centrally at the Coordinating Center through the Study Coordinator or Project Manager. The list of required forms can be found in Section 4.4.

It is recommended that participants begin protocol treatment within 7 business days, and no more than 30 days from registration. Issues that would cause treatment delays should be discussed with the Overall PI. If a participant does not receive protocol therapy following registration, the participant's registration on the study must be canceled. The Study Coordinator should be notified of cancellations as soon as possible.

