5.3 Pre-Treatment Criteria

5.3.1 Cycle 1, Day 1

- Absolute neutrophil count $\geq 1,000/\mu\text{L}$
- Platelets $\geq 75,000/\mu\text{L}$
- Hemoglobin $\geq 8\text{g/dL}$
- Total bilirubin $\leq 1.5 \times$ upper limit of normal (ULN)
- AST(SGOT)/ALT(SGPT) $\leq 3 \times$ institutional ULN without liver metastases, or $\leq 5 \times$ institutional ULN with liver metastases
- Creatinine clearance $\geq 50 \text{ mL/min}$
- Left ventricular ejection fraction $\geq 50\%$, as determined by RVG (MUGA) or echocardiogram(ECHO) within 60 days prior to initiation of protocol therapy

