11.1.3 Methods for Evaluation of Disease

All measurements should be taken and recorded in metric notation using a ruler, calipers, or a digital measurement tool. All baseline evaluations should be performed as closely as possible to the beginning of treatment and never more than 4 weeks before the beginning of the treatment.

The same method of assessment and the same technique should be used to characterize each identified and reported lesion at baseline and during follow-up. Imaging-based evaluation is preferred to evaluation by clinical examination unless the lesion(s) being followed cannot be imaged but are assessable by clinical exam.

Clinical lesions. Clinical lesions will only be considered measurable when they are superficial (*e.g.*, skin nodules and palpable lymph nodes) and ≥ 10 mm in diameter as

assessed using calipers (*e.g.*, skin nodules). In the case of skin lesions, documentation by color photography, including a ruler to estimate the size of the lesion, is recommended.

Conventional CT and MRI. This guideline has defined measurability of lesions on CT scan based on the assumption that CT thickness is 5mm or less. If CT scans have slice thickness greater than 5 mm, the minimum size of a measurable lesion should be twice the slice thickness. MRI is also acceptable in certain situations (*e.g.* for body scans).

Use of MRI remains a complex issue. MRI has excellent contrast, spatial, and temporal resolution; however, there are many image acquisition variables involved in MRI, which greatly impact image quality, lesion conspicuity, and measurement. Furthermore, the availability of MRI is variable globally. As with CT, if an MRI is performed, the technical specifications of the scanning sequences used should be optimized for the evaluation of the type and site of disease. Furthermore, as with CT, the modality used at follow-up should be the same as was used at baseline and the lesions should be measured/assessed on the same pulse sequence. It is beyond the scope of the RECIST guidelines to prescribe specific MRI pulse sequence parameters for all scanners, body parts, and diseases. Ideally, the same type of scanner should be used and the image acquisition protocol should be followed as closely as possible to prior scans. Body scans should be performed with breath-hold scanning techniques, if possible.

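### The only required pregnancy test is timed to registration and is not repeated near the first dose, so at non-DF/HCC sites it can be up to 58 days old when treatment starts

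*Combined protocol and SAP*

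**What the plan says.** - **Test and timing.** Criterion 3.1.9 requires women of childbearing potential, premenopausal women included, to have a negative "urine pregnancy test within 4 weeks of registration". Section 3 places eligibility laboratory tests before registration, and the 4.4 registration packet for other sites includes the pregnancy test result. The four weeks therefore run backwards from registration.
- **Schedule.** Table 7 marks the urine pregnancy test once, under Baseline. Section 5.3.1 lists blood counts, bilirubin, transaminases, creatinine clearance and LVEF for Cycle 1 Day 1, and no pregnancy test.
- **Registration to treatment.** For other investigative sites, 4.3 says: "It is recommended that participants begin protocol treatment within 7 business days, and no more than 30 days from registration". For DF/HCC sites, 4.1 gives no number of days but says: "Issues that would cause treatment delays should be discussed with the Overall Principal Investigator".
- **Imaging.** Section 3 says: "Scans and x-rays must be done ≤ 4 weeks prior to registration". Section 11.1.3 adds that baseline evaluations should be "never more than 4 weeks before the beginning of the treatment".
- **Fetal risk.** Criterion 3.1.10 says: "The effects of neratinib and fulvestrant on the developing human fetus are unknown". It also describes SERD agents as known teratogens. Exclusion 3.2.16 bars pregnant women because of fulvestrant's teratogenic or abortifacient potential.
- **Other safeguards.** Criterion 3.1.10 requires contraception before and during the study, and adds: "Should a woman become pregnant or suspect she is pregnant while she is participating in this study, she should inform her treating physician immediately". Section 7.6 requires pregnancies to be reported within 24 hours of staff learning of them.

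**The concern.** A screening test shows pregnancy status on the day it was taken. The exposure to be prevented begins with the first dose, and the plan allows the two dates to lie well over four weeks apart. If contraception fails in between and the woman does not yet suspect pregnancy, a site following the plan exactly would start treatment on an out-of-date negative result.

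Neratinib is given in both arms, so the gap is not confined to the fulvestrant arm. The LHRH agonist in 5.2 starts with study treatment and gives no cover during the interval.

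The plan does tie other entry conditions to the start of treatment. LVEF must be measured "within 60 days prior to initiation of protocol therapy", and the washout and major-surgery exclusions (3.2.4, 3.2.5) also count back from planned treatment. Pregnancy status is not anchored in this way. What is at stake is participant and fetal safety; the efficacy analysis is not affected.

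**Working it through.** The plan states no maximum test age, so there is no figure to reproduce. The check is calendar arithmetic.

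**Inputs**
- Test: at most 28 days before registration (3.1.9, section 3).
- Registration to treatment at other sites: 7 business days recommended, 30 days at most (4.3).
- Scan: S days before registration, with S from 0 to 28 (section 3).
- Scan to treatment: at most 28 days (11.1.3).

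**Formula.** Maximum test age at first dose = 28 + days from registration to first dose.

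**Recommended start, other sites.** Without public holidays, 7 business days are 9 calendar days for a Monday to Wednesday registration and 11 for a Thursday or Friday.
- 28 + 9 = 37 days
- 28 + 11 = 39 days

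A holiday would add to this.

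**Outer limit in 4.3, taken alone.** 28 + 30 = 58 days.

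**With 11.1.3 applied to imaging and no repeat scan.** A scan S days before registration leaves at most 28 − S days from registration to first dose. A test taken on day −28 is then at most 28 + (28 − S) = 56 − S days old.

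| Scan before registration (S) | Registration to first dose, at most | Test age, at most |
|---|---|---|
| 0 days | 28 days | 56 days |
| 14 days | 14 days | 42 days |
| 28 days | 0 days | 28 days |

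If test and scan are done on the same day, the test is also at most 28 days old. The 37 and 39 day figures are compatible with 11.1.3 only if the scan is no more than 28 − 9 = 19 or 28 − 11 = 17 days before registration.

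**DF/HCC sites.** Section 4.1 supplies no interval, so 4.3's figures cannot be carried over. The imaging rule, if applied, gives the same 56 − S limit there.

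**Test on the day of dosing.** Neither 5.3.1 nor the Cycle 1 Day 1 column of Table 7 has one.

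**The case against.** The strongest case against is that the plan is consistent and the risk is already managed. Sections 3.1.9, 5.3.1 and Table 7 agree with one another, and nothing in the documents sets a test-to-dose limit that is being broken. Contraception is required before the study, suspected pregnancy must be reported at once, delays go to the Overall PI, and Cycle 1 Day 1 includes a physical examination. Harm needs contraceptive failure within a few weeks, no suspicion of pregnancy, and a conception early enough for a Day 1 urine test to show it. All of this stands as a limit on the size of the risk. None of it verifies pregnancy status when dosing starts: contraception is an undertaking, self-report depends on suspicion, and the instruction to discuss delays does not mention retesting.

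Four stronger readings are tempting and should not be made:
- *That no pregnancy test is required before the first dose.* One is: it must precede registration, and registration must precede therapy. What is missing is a repeat close to dosing.
- *That 56 days is a limit the plan sets on the test.* It follows only from a rule placed under methods for disease evaluation, with the scan on the day of registration, no repeat imaging, and dosing 28 days later.
- *That the test age has no bound at DF/HCC sites.* Section 4.1 states none, but 4.2 requires a registration SOP that is not among the documents and may contain one.
- *That 37 to 39 or 58 days is typical.* These are maxima, with the test on the earliest permitted day, and they apply to sites under 4.3.

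In the other direction, 11.1.3 refers to baseline evaluations in general, so a reader might extend it to the pregnancy test. Its place among lesion-measurement instructions points to disease evaluations. Even on the wider reading, a 28-day-old test would be acceptable and no test at dosing would be required.

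**Conclusion.** The concern holds in this form: the one required pregnancy test is timed to registration, and no repeat is required near the first dose. At non-DF/HCC sites its age at first dose can reach 37 to 39 days at the recommended start and 58 days at the 4.3 limit. If 11.1.3 governs imaging and scans are not repeated, the ceiling is 56 − S days.

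These figures assume a test on the earliest allowed day and, for 37 to 39, no public holidays. The documents do not give the number of women of childbearing potential or an expected number of pregnancies, so the number of exposures is not estimated. Sites may also retest under local practice.

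This is a cheap improvement in patient safety. It does not show a contradiction in the plan, and it has no bearing on power or the primary analysis.

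**What to change.** Keep the 3.1.9 test for registration. Add to 5.3.1, for women of childbearing potential, a negative urine pregnancy test before the first dose on Cycle 1 Day 1, and mark Cycle 1 Day 1 in the urine pregnancy test row of Table 7. Section 10 already requires assessments to be done before any study agent is given, so the order needs no further wording.

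The cost is one extra urine test per woman of childbearing potential, at a visit that already has a physical examination, CBC and chemistries, plus two protocol entries. No visit or invasive procedure is added. The test will not detect a very early pregnancy, so the contraception and self-report provisions in 3.1.10 must stay.
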